6.3 Month 3 (Day 84)

Site staff will provide subjects with meals and snacks at appropriate times during the visit. Where possible and applicable the 12MWT should be performed at the same time of day as in the Week 24 Visit of the STRIDE study. A sample Schedule for Study Visit is in [Appendix 5](#).

The urine and blood samples should be carried out **prior to dosing**:

- Obtain urine sample for:
 - Urinalysis (and pregnancy testing if WOCBP)
- Obtain blood samples for:
 - Pre-dose plasma sample for PK analysis of REN001
 - Haematology and biochemistry
 - FSH test for females (if menopausal symptoms develop)

Following these tests, the study drug should be administered with food under the supervision of clinical staff and the time of dosing recorded.

- Plasma samples for PK analysis of REN001 will be taken at 1, 2, and 4 hours post dose. Other assessments below should be scheduled in between blood samples. Exact time of collection of all blood samples to be recorded.

Other assessment to be performed at this visit:

- Review concomitant medications, non-drug treatments and study drug compliance including capsule counts of remaining study drug.
- Review of AEs.
- Brief physical examination (including weight).
- ECG.
- Vital signs (including temperature).
- PRO Questionnaires (to be completed prior to exercise testing)
 - MFIS
 - PGIS – muscle symptoms and fatigue symptoms
 - PROMIS Short Form – 13a (FACIT Fatigue)
 - SF-36
 - WPAI:SHP

- 12MWT (to be completed at the same time of day as previously).
- Eye examination (may be completed \pm 14 days of the visit if required).
- Provide home pregnancy testing kits for WOCBP for use at Months 4 and 5 of dosing. Study centre will telephone the subject and remind them of the need to complete the test and confirm the test has been carried out. The date of test and result will be recorded in the eCRF.
- Provide a urine collection cup and instructions for collecting a second morning void for next study visit. This is provided in case the subject has their second morning void before attending the study centre at their next study visit.
- Dispense study drug and remind subject of study drug dosing requirements and study restrictions.

6.4 Month 6 (Day 168)

Site staff will provide subject with meals and snacks at appropriate times during the visit. The following assessments will be carried out:

- The subject should take their study drug with food at their usual dosing time. The actual time of dosing should be recorded by the patient on a dosing card.
- Obtain second morning void urine sample for:
 - Bone marker – NTX
 - Urinalysis and drugs of abuse testing
 - Urine pregnancy testing (WOCBP)
- Obtain blood samples for:
 - Haematology and biochemistry
 - Bone and calcium metabolism markers
 - 2 plasma samples for PK analysis of REN001, sample 1 to be taken on arrival at site, sample 2 to be taken at end of visit. Time of samples to be recorded.
 - FSH test for females (if menopausal symptoms develop)
- Review concomitant medications, non-drug treatments and study drug compliance including capsule counts of remaining study drug.
- Review of AEs.
- Physician completion of subject's PMM phenotypic description.
- Brief physical examination (including weight).
- ECG.
- Vital signs (including temperature).
- PRO Questionnaires (to be completed prior to exercise testing)
 - MFIS
 - PGIS – muscle symptoms and fatigue symptoms
 - PROMIS Short Form – 13a (FACIT Fatigue)
 - SF-36
 - WPAI:SHP
- 12MWT (to be completed at same time of day as previously).
- Eye examination (may be completed \pm 14 days of the visit if required).
- Provide home pregnancy testing kits for WOCBP to enable monthly pregnancy

testing. Study centre will telephone the subject and remind them of the need to complete the test and confirm the test has been carried out each month. The date of test and result will be recorded in the eCRF.

- Provide a urine collection cup and instructions for collecting a second morning void for next study visit. This is provided in case the subject has their second morning void before attending the study centre at their Month 12 study visit.
- Dispense study drug and remind subject of study drug dosing requirements and study restrictions.

6.5 Month 9 (Day 252) – German sites only

Site staff will provide subject with meals and snacks at appropriate times during the visit. The following assessments will be carried out:

- The subject should take their study drug with food at their usual dosing time. The actual time of dosing should be recorded by the patient on a dosing card.
- Urinalysis and drugs of abuse testing
- Urine pregnancy testing (WOCBP)
- Obtain blood samples for:
 - Haematology and biochemistry
 - FSH test for females (if menopausal symptoms develop)
- Review concomitant medications, non-drug treatments and study drug compliance including capsule counts of remaining study drug.
- Review of AEs.
- Brief physical examination (including weight).
- ECG.
- Vital signs (including temperature).
- Provide home pregnancy testing kits for WOCBP to enable monthly pregnancy testing. Study centre will telephone the subject and remind them of the need to complete the test and confirm the test has been carried out each month. The date of test and result will be recorded in the eCRF.

6.6 Month 12 (Day 336)

Site staff will provide subjects with meals and snacks at appropriate times during the visit. The following assessments will be carried out:

- The subject should take their study drug with food at their usual dosing time. The time of dosing should be recorded by the patient on a dosing card.
- Obtain second morning void urine sample for:
 - Bone marker – NTX
 - Urinalysis and drugs of abuse testing
 - Urine pregnancy testing (WOCBP)
- Obtain blood samples for:
 - Haematology and biochemistry (including HbA1c)
 - Bone and calcium metabolism markers
 - 2 plasma samples for PK analysis of REN001, sample 1 to be taken on arrival at site, sample 2 to be taken at end of visit. Time of sample collection to be

- recorded.
- FSH test for females (if menopausal symptoms develop)
- Review concomitant medications, non-drug treatments and study drug compliance including capsule counts of remaining study drug.
- Review of AEs.
- Physician completion of subject's PMM phenotypic description.
- Brief physical examination (including weight).
- ECG.
- Vital signs (including temperature).
- PRO Questionnaires (to be completed prior to exercise testing)
 - MFIS
 - PGIS – muscle symptoms and fatigue symptoms
 - PROMIS Short Form – 13a (FACIT Fatigue)
 - SF-36
 - WPAI:SHP
 - PGIC muscle and fatigue symptoms
 - BPI
- 12MWT (to be completed at same time of day as previously).
- Eye examination (may be completed \pm 14 days of the visit if required).
- Provide home pregnancy testing kits for WOCBP to enable monthly pregnancy testing. Study centre will telephone the subject and remind them of the need to complete the test and confirm the test has been carried out each month. The date of test and result will be recorded in the eCRF.
- Provide a urine collection cup and instructions for collecting a second morning void for next study visit. This is provided in case the subject has their second morning void before attending the study centre at their Month 18 study visit.
- Dispense study drug and remind subject of study drug dosing requirements and study restrictions.

6.7 Month 15 (Day 420) – Germany only

Site staff will provide subject with meals and snacks at appropriate times during the visit. The following assessments will be carried out:

- The subject should take their study drug with food at their usual dosing time. The actual time of dosing should be recorded by the patient on a dosing card.
- Urinalysis and drugs of abuse testing
- Urine pregnancy testing (WOCBP)
- Blood samples for:
 - Haematology and biochemistry
 - FSH test for females (if menopausal symptoms develop)
- Review concomitant medications, non-drug treatments and study drug compliance including capsule counts of remaining study drug.
- Review of AEs.

- Brief physical examination (including weight).
- ECG.
- Vital signs (including temperature).
- Provide home pregnancy testing kits for WOCBP to enable monthly pregnancy testing. Study centre will telephone the subject and remind them of the need to complete the test and confirm the test has been carried out each month. The date of test and result will be recorded in the eCRF.

6.8 Month 18 (Day 504)

Site staff will need to provide subject with meals and snacks at appropriate times during the visit. The following assessments will be carried out:

- The subject should take their study drug with food at their usual dosing time. The time of dosing should be recorded by the patient on a dosing card.
- Obtain second morning void urine sample for:
 - Bone marker – NTX
 - Urinalysis and drugs of abuse testing
 - Pregnancy testing (WOCBP)
- Obtain blood samples for:
 - Haematology and biochemistry
 - Additional bone and calcium metabolism markers
 - 2 plasma samples for PK analysis of REN001, sample 1 to be taken on arrival at site, sample 2 to be taken at end of visit. Time of samples to be recorded.
 - FSH test for females (if menopausal symptoms develop)
- Review concomitant medications, non-drug treatments and study drug compliance including capsule counts of remaining study drug.
- Review of AEs.
- Brief physical examination (including weight).
- ECG.
- Vital signs (including temperature).
- PRO Questionnaires (to be completed prior to exercise testing):
 - MFIS
 - PGIS – muscle symptoms and fatigue symptoms
 - PROMIS Short Form – 13a (FACIT Fatigue)
 - SF-36
 - WPAI:SHP
- 12MWT (to be completed at same time of day as previously).
- Eye examination (may be completed \pm 14 days of the visit if required).
- Provide home pregnancy testing kits for WOCBP to enable monthly pregnancy testing. Study centre will telephone the subject and remind them of the need to complete the test and confirm the test has been carried out each month. The date of test and result will be recorded in the eCRF.

- Provide a urine collection cup and instructions for collecting a second morning void for next study visit. This is provided in case the subject has their second morning void before attending the study centre at their next study visit.
- Dispense study drug and remind subject of study drug dosing requirements and study restrictions.

6.9 Month 24 (Day 672) or Early Withdrawal Visit (Prior to Month 24)

Site staff will provide subjects with meals and snacks at appropriate times during the visit.

If the subject discontinues study treatment prior to Month 24 they will be withdrawn from the study. If they discontinue study treatment between visits, they will be required to attend an early withdrawal visit as soon as possible after their last dose of REN001. If their withdrawal is prior to the Month 24 visit, the below assessments should be carried out:

The following assessments will be carried out:

- The subject should take their study drug with food at their usual dosing time. The actual time of dosing should be recorded by the patient on a dosing card.
- Obtain second morning void urine sample for:
 - Bone marker – NTX
 - Urinalysis and drugs of abuse testing
 - Pregnancy testing (WOCBP)
- Obtain blood samples for:
 - Haematology and biochemistry (including HbA1c)
 - Bone and calcium metabolism markers
 - 2 plasma samples for PK analysis of REN001, sample 1 to be taken on arrival at site, sample 2 to be taken at end of visit. Time of samples to be recorded.
 - FSH test for females (if menopausal symptoms develop)
- Review concomitant medications, non-drug treatments and study drug compliance including capsule counts of remaining study drug.
- Review of AEs.
- Physician completion of subject's PMM phenotypic description.
- Brief physical examination (including weight).
- ECG.
- Vital signs (including temperature).
- PRO Questionnaires (to be completed prior to exercise testing)
 - MFIS
 - PGIS – muscle symptoms and fatigue symptoms
 - PROMIS Short Form – 13a (FACIT Fatigue)
 - SF-36
 - WPAI:SHP
 - PGIC muscle and fatigue symptoms
 - BPI
- 12MWT (to be completed at same time of day as previous visits).
- Eye examination (may be completed \pm 14 days of the visit if required).

- Optional DXA Scan
 - Eligible subjects must have had a DXA scan at baseline, either as part of the STRIDE study or at entry into this long-term safety study. If subject is an Early Withdrawal, a scan will only be performed if there has been at least 20 weeks of dosing following the baseline scan. All female subjects not confirmed as post-menopausal should have an FSH test performed. All WOCBP must have a negative pregnancy test prior to the scan. Where possible, the same scanner should be used at this visit as at the baseline visit. Details can be found in the DXA Manual.

The following items must be completed for subjects continuing dosing beyond Month 24:

- Provide home pregnancy testing kits for WOCBP to enable monthly pregnancy testing. Study centre will telephone the subject and remind them of the need to complete the test and confirm the test has been carried out each month. The date of test and result will be recorded in the eCRF.
- Provide a urine collection cup and instructions for collecting a second morning void for next study visit. This is provided in case the subject has their second morning void before attending the study centre at their Month 30 study visit.
- Dispense study drug and remind subject of study drug dosing requirements and study restrictions.

6.10 Month 30 (Day 840)

Site staff will need to provide subject with meals and snacks at appropriate times during the visit. The following assessments will be carried out:

- The subject should take their study drug with food at their usual dosing time. The time of dosing should be recorded by the patient on a dosing card.
- Obtain second morning void urine sample for:
 - Bone marker – NTX
 - Urinalysis and drugs of abuse testing
 - Pregnancy testing (WOCBP)
- Obtain blood samples for:
 - Haematology and biochemistry
 - Additional bone and calcium metabolism markers
 - FSH test for females (if menopausal symptoms develop)
- Review concomitant medications, non-drug treatments and study drug compliance including capsule counts of remaining study drug.
- Review of AEs.
- Brief physical examination (including weight).
- ECG.
- Vital signs (including temperature).
- PRO Questionnaire:
 - PGIS – muscle symptoms and fatigue symptoms
- Eye examination (may be completed \pm 14 days of the visit if required).
- Provide home pregnancy testing kits for WOCBP to enable monthly pregnancy testing. Study centre will telephone the subject and remind them of the need to

complete the test and confirm the test has been carried out each month. The date of test and result will be recorded in the eCRF.

- Provide a urine collection cup and instructions for collecting a second morning void for next study visit. This is provided in case the subject has their second morning void before attending the study centre at their Month 36 study visit.
- Dispense study drug and remind subject of study drug dosing requirements and study restrictions.

6.11 Month 36 (Day 1008)

Site staff will need to provide subject with meals and snacks at appropriate times during the visit. The following assessments will be carried out:

- The subject should take their study drug with food at their usual dosing time. The time of dosing should be recorded by the patient on a dosing card.
- Obtain second morning void urine sample for:
 - Bone marker – NTX
 - Urinalysis and drugs of abuse
 - Pregnancy testing (WOCBP)
- Obtain blood samples for:
 - Haematology and biochemistry
 - Additional bone and calcium metabolism markers
 - FSH test for females (if menopausal symptoms develop)
- Review concomitant medications, non-drug treatments and study drug compliance including capsule counts of remaining study drug.
- Review of AEs.
- Brief physical examination (including weight).
- ECG.
- Vital signs (including temperature).
- PRO Questionnaire:
 - PGIS – muscle symptoms and fatigue symptoms
 - PGIC – muscle symptoms and fatigue symptoms
- Eye examination (may be completed \pm 14 days of the visit if required).
- Provide home pregnancy testing kits for WOCBP to enable monthly pregnancy testing. Study centre will telephone the subject and remind them of the need to complete the test and confirm the test has been carried out each month. The date of test and result will be recorded in the eCRF.
- Provide a urine collection cup and instructions for collecting a second morning void for next study visit. This is provided in case the subject has their second morning void before attending the study centre at their Month 42 study visit.
- Dispense study drug and remind subject of study drug dosing requirements and study restrictions.

6.12 Month 42 (Day 1176)

Site staff will need to provide subject with meals and snacks at appropriate times during the visit. The following assessments will be carried out:

- The subject should take their study drug with food at their usual dosing time. The time of dosing should be recorded by the patient on a dosing card.
- Obtain second morning void urine sample for:
 - Bone marker – NTX
 - Urinalysis and drugs of abuse
 - Pregnancy testing (WOCBP)
- Obtain blood samples for:
 - Haematology and biochemistry
 - Additional bone and calcium metabolism markers
 - FSH test for females (if menopausal symptoms develop)
- Review concomitant medications, non-drug treatments and study drug compliance including capsule counts of remaining study drug.
- Review of AEs.
- Brief physical examination (including weight).
- ECG.
- Vital signs (including temperature).
- PRO Questionnaire:
 - PGIS – muscle symptoms and fatigue symptoms
- Eye examination (may be completed \pm 14 days of the visit if required).
- Provide home pregnancy testing kits for WOCBP to enable monthly pregnancy testing. Study centre will telephone the subject and remind them of the need to complete the test and confirm the test has been carried out each month. The date of test and result will be recorded in the eCRF.
- Provide a urine collection cup and instructions for collecting a second morning void for next study visit. This is provided in case the subject has their second morning void before attending the study centre at their Month 48 study visit.
- Dispense study drug and remind subject of study drug dosing requirements and study restrictions.

6.13 Month 48 (Day 1344) or Early Withdrawal Visit (Post Month 24)

Site staff will need to provide subject with meals and snacks at appropriate times during the visit.

If the subject discontinues study treatment prior to Month 48 they will be withdrawn from the study. If they discontinue study treatment between visits, they will be required to attend an early withdrawal visit as soon as possible after their last dose of REN001. If their withdrawal is after the Month 24 visit, the below assessments should be carried out. The following assessments will be carried out:

- The subject should take their study drug with food at their usual dosing time. The time of dosing should be recorded by the patient on a dosing card.
- Obtain second morning void urine sample for:
 - Bone marker – NTX
 - Urinalysis and drugs of abuse

- Pregnancy testing (WOCBP)
- Obtain blood samples for:
 - Haematology and biochemistry
 - Additional bone and calcium metabolism markers
 - FSH test for females (if menopausal symptoms develop)
- Review concomitant medications, non-drug treatments and study drug compliance including capsule counts of remaining study drug.
- Review of AEs.
- Brief physical examination (including weight).
- ECG.
- Vital signs (including temperature).
- PRO Questionnaires:
 - PGIS – muscle symptoms and fatigue symptoms
 - PGIC – muscle symptoms and fatigue symptoms
- Eye examination (may be completed \pm 14 days of the visit if required).
- Optional DXA Scan
 - Eligible subjects must have had a DXA scan at baseline and/or at the Month 24 visit. If subject is an Early Withdrawal after M24, a scan will only be performed if there has been at least 20 weeks of dosing following the M24 scan. All female subjects not confirmed as post-menopausal should have an FSH test performed. All WOCBP must have a negative pregnancy test prior to the scan. Where possible, the same scanner should be used at this visit as at the baseline and Month 24 visits. Details can be found in the DXA Manual.
- Provide home pregnancy testing kit for WOCBP for final pregnancy test prior to the follow-up telephone contact at approximately 30 days after the last dose of study drug.

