6.1.3.1 Screening Visit

- Obtain written informed consent. Subjects should be given adequate time to think about whether they want to participate and to ask questions. The Investigator (or an appropriate delegate at the site) will obtain written consent from each subject prior to commencing any specific study related activities or assessments.
- Subject Demography.
- Complete Medical History (including prescription and non-prescription drugs/treatment, non-drug treatments, topical products, vitamins and dietary supplements taken in the last 4 weeks, alcohol, drugs of abuse and tobacco use. (See [Table 1](#) for prohibited medication and washout times).
- Review of ongoing concomitant medications and non-drug treatments. If subject is on any prohibited medications ([Table 1](#)), a washout period will be required and the baseline visit should be scheduled after the washout period.
- Review of pre-treatment events ([Section 7.1.1.1](#)).
- Full physical examination (including weight and height).
- ECG.
- Vital signs (including temperature).
- Urinalysis and drugs of abuse testing.
- Blood samples for:
 - Haematology and biochemistry (including HbA1c, HIV/Hepatitis B/C serology)
 - Serum pregnancy test (WOCBP)
 - Serum FSH testing for all females (≥ 45 years) enrolling from Study REN001-101 (UK only) or not confirmed as post-menopausal in the STRIDE study
- Eye examination (may be completed between Screening and Baseline visits). Eye examinations will not be repeated if within 6 months of a previous test within STRIDE.
- Optional DXA Scan (in those countries and sites where this is permitted). It should be scheduled as close as possible to the baseline visit, however if this is not feasible, then it must be performed within the 4 weeks after the baseline visit. Subjects must be checked against the Additional Criteria for Sites with approvals for DXA Scans ([Section 4.4](#)). All WOCBP must have a negative pregnancy test prior to the scan. All female subjects will require an FSH test if not confirmed as post-menopausal on the STRIDE Study. A STRIDE subject will not have a baseline DXA in this study if they had a Week 24 DXA in the STRIDE study. Details of how the DXA scan will be performed can be found in the DXA Manual. DXA scans will not be repeated if within 6 months of a previous scan within STRIDE.

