7.1.7 Dual-energy X-ray absorptiometry (DXA) Scans

Eligible subjects can choose to have a DXA scan (in those countries and sites where this is permitted), of the non-dominant hip and spine. If the non-dominant hip is unsuitable for scanning (e.g., fractures, hip replacement etc.) then the dominant hip can be used instead.

The same DXA scanner should be used for all scans on an individual subject to aid interpretation of the scans. Subject weight and height are required for scan data, further details can be found in the DXA Scanning Manual. Scans which are not of sufficient quality, as determined by an independent assessor, will not be included in the database.

DXA scans will not be repeated if within 6 months of a previous test within STRIDE.

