3.5. DETERMINATION OF SAMPLE SIZE

The sample size for this study is not based on statistical justification. Recruitment of mtDNA-PMM subjects will be limited to those subjects who participated in REN001-201 or REN001-101, and reside in countries where this long-term safety study is approved. It is estimated that approximately 150 mtDNA-PMM subjects will be enrolled.

It is anticipated that up to 50 nDNA-PMM subjects may also be enrolled.

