3. (a) REN001-201 Exit

Enrolment after exiting REN001-201 will result in a break in study participation of variable duration where the subject is off study drug and not monitored in either study. Due to the gap in monitoring and dosing, for reporting purposes, the subject's two participations will be considered as two separate subjects and data in REN001-202 will not be considered as a continuation from REN001-201.

These subjects will need to complete Screening and Baseline visits in REN001-202 to check eligibility prior to enrolment. If the subject had a DXA scan in REN001-201, then the REN001-201 Week 24 visit can be used as the Baseline assessment if there is 6 months or less since the assessment. Similarly, the REN001-201 Week 24 eye examination can be used as the Baseline assessment if there is a gap of 6 months or less.

Dosing in REN001-202 will start on the day of the REN001-202 Baseline visit.

The schematic below details how subjects transition between the 2 studies:

REN001-201 Treatment Group	REN001-201								Break in study participation	REN001-202							
	Sc	BL	W2	W4	W12	W18	W24	FU		Sc	BL	M1	M3	M6	M12	M18	M24
REN001	REN001									REN001 [^]							
	Sc	BL	M0.5	M1	M3	M4.5	M6	FU		Sc	BL	M1	M3	M6	M12	M18	M24
Placebo	Placebo									REN001							
	Sc	BL	M0.5	W4	W12	W18	W24	FU		Sc	BL	M1	M3	M6	M12	M18	M24

Footnote: Sc=Screening; BL=Baseline; FU=Follow-up; W=Week; M=Month.

[^] Data from REN001-202 will not be considered a continuation of REN001-201 but will be reported as a separate subject. In REN001-202 visits occur every 6 months between Month 24 and Month 48 (i.e., Months 30, 36 and 42). Where applicable, a final follow up telephone call will occur approximately 30 days after the last dose of study drug.

3. (b) REN001-101

REN001-101 completed in March 2020 and therefore subjects will not have received mavodelpar for more than 2 years at the time of entry to REN001-202. For reporting purposes, only data from the start of REN001-202 will be considered.

Subjects will need to perform Screening and Baseline visits in REN001-202 to check eligibility prior to enrolment.

Dosing in REN001-202 will start on the day of the REN001-202 Baseline visit.

The schematic below details the subject visits:

REN001-201 Treatment Group	REN001-201								REN001-202							
	Sc	BL	W2	W4	W12	W18	W24	FU	Sc	BL	M1	M3	M6	M12	M18	M24
NA	Not Applicable								REN001							
									Sc	BL	M1	M3	M6	M12	M18	M24

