8. GENERAL ASPECTS FOR STATISTICAL ANALYSIS

8.1. HYPOTHESIS TESTING

No formal statistical testing is planned.

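### The DXA rules conflict on the withdrawal scan after Month 24 and on the baseline scan for late re-entrants from STRIDE, so some changes in bone density would be lost or distorted

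*Protocol*

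**What the plan says.** The bone endpoint is change in bone mineral density from baseline to end of treatment (Protocol 3.2.4, SAP 3.2.4). Scans are optional for all subjects (Protocol 4.4).

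**Withdrawal scan.** For subjects who stop before Month 24, Protocol 6.9 says that "a scan will only be performed if there has been at least 20 weeks of dosing following the baseline scan". For those who stop later, Protocol 6.13 opens with "Eligible subjects must have had a DXA scan at baseline and/or at the Month 24 visit" and continues that "a scan will only be performed if there has been at least 20 weeks of dosing following the M24 scan". Protocol 4.4 provides a scan at early withdrawal with no dosing condition. SAP 6.3 asks only for 20 weeks of study drug, not tied to any scan. Protocol Table 3 footnote 9 requires a baseline scan.

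**Baseline for subjects who exit STRIDE and re-enter.** Protocol 6.1.3.1 says "A STRIDE subject will not have a baseline DXA in this study if they had a Week 24 DXA in the STRIDE study", with no time limit. The last sentence of the same bullet waives a repeat only within 6 months of a STRIDE scan. Protocol 4.4 and the Table 2 DXA footnote (repeated as footnote 14 in SAP 3.4) take the Week 24 scan as baseline without limit. SAP 3.8, item 3(a), says "the REN001-201 Week 24 visit can be used as the Baseline assessment if there is 6 months or less since the assessment", and SAP 6.3 waives a new scan only within 6 months. SAP 8.6 takes the last non-missing assessment before dosing and sets no limit on its age.

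**The concern.** A change from baseline needs both a baseline scan and a later one. The first conflict can remove the later scan, and the second can remove or distort the baseline.

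The first loss is selective. A subject with only a baseline scan who completes Month 48 is scanned under 6.13, because the eligibility sentence covers that subject. A subject with the same scan history who stops shortly before is not. The missing values therefore fall on subjects who stopped treatment after long exposure, so the loss may be informative.

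Protocol 1.4.2.6 says it is not known whether REN001 affects bone density, notes bone loss with PPARγ agonists, and relies on DXA where available. The data come only from subjects who opt in at participating sites, so avoidable losses matter. A baseline scan not taken before dosing restarts cannot be recovered.

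**Working it through.** There is no power or precision figure to reproduce: "The sample size for this study is not based on statistical justification". The check applies each rule to the same hypothetical subject, using the plan's visit days (Month 24 = Day 672, Month 48 = Day 1344, 20 weeks = 140 days, window ±21 days) and 365.25 days to the year.

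**1. Baseline scan, no Month 24 scan, stops after Month 24**

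| Source | Condition for a withdrawal scan | Result |
|---|---|---|
| Protocol 4.4 | No dosing condition | Scanned |
| Protocol 6.13 | 20 weeks of dosing after the Month 24 scan | Never met, because there is no such scan |
| SAP 6.3 | 20 weeks of study drug | Scanned, since 673 ≥ 140 |

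- Possible stop days are 673 to 1343, which is 1343 − 673 + 1 = 671 days. In years: 673/365.25 = 1.84 and 1343/365.25 = 3.68.
- If the Month 24 visit falls at either end of its window (Day 651 or 693), the range starts at Day 652 (1.79 years) or Day 694 (1.90 years).
- More than 2 calendar years in this study applies from Day 731, which is 1343 − 731 + 1 = 613 of the 671 days.
- By contrast, a subject who stops about 140 days after the baseline scan is scanned under 6.9.
- SAP 7.5 defines the DXA set by a valid Month 24, Month 48 or early termination scan. The subject above has none of these and leaves the set.
- Protocol 6.9 allows the Month 24 scan only for subjects who already have a baseline scan. The and/or wording in 6.13 therefore adds nobody except subjects with a baseline scan and no Month 24 scan, which is the group that the next sentence shuts out at withdrawal.

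A subject who did have the Month 24 scan on Day 672 and stops before Day 672 + 140 = 812 also gets no later scan under 6.13, but keeps the Month 24 value and stays in the set.

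**2. STRIDE Week 24 scan, exits STRIDE, re-enters more than 6 months after the scan**

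| Source | Treatment of the old scan |
|---|---|
| Protocol 6.1.3.1, sentence on the Week 24 scan | No new baseline scan, no time limit |
| Protocol 4.4; Table 2 footnote; SAP 3.4 footnote 14 | Old scan is the baseline, no time limit |
| Protocol 6.1.3.1, sentence on repeats; SAP 6.3 | Waiver of a new scan limited to 6 months |
| SAP 3.8, item 3(a) | Accepted only if 6 months old or less |
| SAP 8.6 | Accepted at any age |

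- SAP 3.8 describes the break as variable in length and gives no maximum, so scans older than 6 months are possible.
- STRIDE follow-up is 21 to 28 days after the last dose (SAP Appendix 2). Assume the scan was on the day of the last dose, and take 6 months as 168 to 183 days. The limit is then passed between 168 − 28 = 140 and 183 − 21 = 162 days after STRIDE follow-up.
- A site that follows the unlimited sentence takes no new scan. Under SAP 3.8 the subject then has no baseline and no change value, but stays in the DXA set, which does not require a baseline. Under SAP 8.6 the old scan is used, and the change includes the period off study drug and outside both studies.

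**The case against.** The strongest reply is that other text rescues these subjects. Protocol 4.4 and SAP 6.3 would scan the subject who stops after Month 24. A site that applies the 6-month sentence in 6.1.3.1 would rescan the late re-entrant. This stands as far as it goes: the loss is not certain, and it depends on which passage a site follows. But 6.13 is the visit-specific instruction, and its condition is impossible for a group that its own bullet admits. The DXA Manual, which might resolve this, is not among the documents.

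A second reply is that little hangs on it. DXA is exploratory, "No formal statistical testing is planned", fractures are captured as events of special interest, and bone markers are taken at the withdrawal visit. This limits the importance of the point but does not remove the conflict.

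A reader might also infer three stronger things that the documents do not support:

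- *Everyone affected has more than 2 years on drug.* Month 24 is Day 672, or 1.84 years. The phrase holds in this study only from Day 731, or when STRIDE exposure to mavodelpar is added (673 + 168 = 841 days, 2.30 years).
- *Late re-entrants have no baseline that the SAP accepts.* SAP 8.6 would accept the old scan. The SAP disagrees with itself rather than rejecting the scan outright.
- *Protocol 7.1.7 bars withdrawal scans soon after rollover*, because it says "DXA scans will not be repeated if within 6 months of a previous test within STRIDE". Protocol 7.1.6 uses the same sentence for eye examinations. Read literally, it would cancel the scheduled Month 3 examination for subjects who roll over at STRIDE Week 24. SAP 6.3 ties the 6 months to the baseline of Exit subjects. The sensible reading is a baseline waiver, so there is no real conflict with 6.9.

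Nothing in the documents shows that subjects would stop because of bone loss; that remains a possibility only.

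**Conclusion.** The point holds for two conflicts. First, if 6.13 is followed, a subject with a baseline scan and no Month 24 scan who stops on Days 673 to 1343 contributes nothing to the bone endpoint, although Protocol 4.4 and SAP 6.3 would have provided a scan. Second, a STRIDE Exit subject whose Week 24 scan is more than 6 months old may have no change value, or one that spans an unmonitored gap, depending on which passage the site and the programmer follow.

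The number affected cannot be computed. The documents give no figures for DXA participation, missed Month 24 scans or late re-entry. It is probably small, since most STRIDE subjects are expected to roll over at Week 24. No primary endpoint changes. The correction is worth making because the endpoint is stated, the data are already sparse and the edits are cheap.

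**What to change.** **Withdrawal scan.** In Protocol 6.13, count the 20 weeks of dosing from the subject's most recent DXA scan instead of from the Month 24 scan. Align Protocol 4.4, Table 3 footnote 9 (repeated in SAP 3.4) and SAP 6.3 with that wording, so that one eligibility condition and one dosing condition apply throughout.

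**Exit baseline.** In Protocol 6.1.3.1, delete the sentence that rules out a new baseline scan after any STRIDE Week 24 scan, and keep the 6-month sentence. Add the same limit for Exit subjects to Protocol 4.4, the Table 2 DXA footnote and SAP 3.4 footnote 14. State in SAP 8.6 that the limit in SAP 3.8 governs the DXA baseline of Exit subjects.

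**Clarification.** Protocol 7.1.7 could say that its 6-month sentence concerns baseline scans.

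Editing 6.13 and 6.1.3.1 alone would leave conflicting text in 4.4, the table footnotes and the SAP. The cost is this set of wording changes and a few more optional scans of a type already planned.
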